9.1.1. Assessment of Errors in Use of Device

Within each sub-study, subjects will be randomised for the order of treatment. One treatment will require subjects to demonstrate use of a single inhaler (ELLIPTA), while the other treatment will require the subject to demonstrate use of 2 inhalers (DISKUS-HandiHaler in Sub Study 1 or Turbuhaler-HandiHaler in Sub Study 2).

Subjects will be provided with the relevant section of the PIL, explaining correct use, for each inhaler they are to be tested on. The critical and over all errors per inhaler and how these have been defined are included in Appendix 2.

The errors listed will be in aligned with the correct use information from the respective PILs, in a checklist for each inhaler and these will be provided to HCPs for scoring errors during the study conduct. The checklists will be provided in the Study Reference Manual.

Figure 2 depicts the process flow for assessing inhaler use errors and further details are provided, for each treatment, in Section 9.1.1.1 and Section 9.1.1.2.

Figure 2 Assessment of errors in use for each DPI tested**9.1.1.1. Assessment of ELLIPTA error in use**

Subject will be asked to read the patient instruction leaflet for ELLIPTA and then demonstrate ELLIPTA use. Any errors (critical or non-critical) made by the subject while using the ELLIPTA will be recorded by the HCP on the checklist provided. If the subject makes no errors, this will also be recorded by the HCP, and there will be no further assessments. If the subject makes any error in the use of the ELLIPTA, the HCP will provide instruction in the correct use of the ELLIPTA to the subject. The subject will then demonstrate ELLIPTA use again. If the subject makes no errors, this will be recorded by the HCP and there will be no further assessments. If the subject again makes errors in the use of the ELLIPTA any errors will be recorded by the HCP. The HCP will again provide instruction in the correct use for the final time, following which the subject will then demonstrate ELLIPTA use one final time. Any errors made during this demonstration will be recorded. There will be no further assessments. In total, the HCP can provide instruction in the use of the inhaler up to two times.

9.1.1.2. Assessment of DISKUS-HandiHaler in Sub Study 1, or Turbuhaler-HandiHaler in Sub Study 2, for error in use

Subjects will be provided with 2 inhalers and 2 PILs dependent on which sub study they are included in.

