9.1.1.3. Time Taken to Use Device

Time taken to use the device will be recorded as follows:

- T1: the time from when the subject starts to read the patient instruction leaflet until they have completed demonstration of device use (i.e., with no investigator support).
- T2: the time from when the HCP starts to instruct subject until correct use is demonstrated (up to a maximum of two attempts only).
- T1+T2: the time from when the subject starts to read the patient information leaflet until correct use is demonstrated (up to a maximum of three attempts, once after reading the PIL and following instruction, up to 2 times, by HCP).

The HCP will start recording (clock start) the time from when T1 begins and will stop when device use has been demonstrated. The clock re-starts when T2 begins and stops once correct use has been demonstrated, or when three failed attempts have been made. Note: T2 includes the time used by the investigator for re-instructing the Subjects throughout.

For subjects who demonstrate correct inhaler use after reading the PIL, T2 will be 0.

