8.1.2.4. Training/Teaching time required

Secondary Statistical Analyses
Endpoint(s)

 Total demonstration time (T1+T2)
Model Specification

 The endpoint of training/teaching time will be analysed using the Intent-to-treat population. This endpoint will be analysed using Kaplan-Meier analysis.
Model Results Presentation

 For DISKUS + HandiHaler or Turbuhaler + HandiHaler the time for each device will be added together to form the total time needed to demonstrate correct use at T1 and T2 respectively. Median time to correctly use the inhaler after reading the patient information leaflet and HCP's instruction (T1+T2) will be presented for each inhaler group. For subjects who correctly used the inhaler after reading the patient information leaflet set T2=0. T1+T2 is censored for subjects who did not use the inhaler correctly after 3 attempts. Kaplan-Meier survivor functions of T1+T2 will be obtained for each inhaler group and plotted on the same figure. In the above analysis the median time will be taken from the Kaplan Meier model.
SAS Code

 Kaplan-Meier survivor functions of the proportion of subjects with a time to correctly use the inhaler will be obtained for each inhaler group separately and will be plotted on the same figure. The following SAS code will be used: <pre>ods output ProductLimitEstimates = plest(keep = trtcd timeto failed left) quartiles=median CensoredSummary=cen; proc lifetest data=t_device outsurv=survest; time timeto*event(0); strata treatment; run;</pre>

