Number of Subjects who failed to demonstrate correct use (censored)	XXX	XXX
Median Time to demonstrate correct inhaler use (minutes) [1]	XXX	XXX

[1] The Median Time to demonstrate correct inhaler use (minutes) is taken from the Kaplan-Meier analysis. If more than 50% of the data is censored then the median is not applicable.
Note: For the Diskus+Handihaler and Turbuhaler +HandiHaler groups, if a subject made an error on one device and not the other the time to demonstrate correct use is censored at the total of time taken for both devices.

Programming notes: Page by sub-study and assessment (Time taken to read the PIL and Demonstrate Correct Use/ Time for HCP Instruction and to Demonstrate Correct Use /Total Time to demonstrate correct use).

Example : EFF_T03
Protocol : 206215
Population : Intent to Treat

Table X.X
Summary and Analysis of Treatment Preference

Sub-study 1: ELLIPTA vs DISKUS + HandiHaler

	Total (N=XXX)	P-Value

Which treatment do you prefer based on the number of the number of steps needed to take your medication?		
n	XXX	X.XXX
ELLIPTA	XXX (XX%)	
DISKUS + HandiHaler	XXX (XX%)	
No Preference	XXX (XX%)	
Which treatment do you prefer for taking your medication?		
n	XXX	X.XXX
ELLIPTA	XXX (XX%)	
DISKUS + HandiHaler	XXX (XX%)	
No Preference	XXX (XX%)	

Note: The p-value is from the Cochran-Mantel-Haenszel Test.
Programming notes: Page by sub-study. %'s calculated out of the small n for each question.

Example : EFF_T04
Protocol : 206215
Population : Intent to Treat

Table X.X
Analysis of Percentage of Subjects making at least one Critical Error

Sub-study 1: ELLIPTA vs DISKUS + HandiHaler
Assessment: After reading the PIL(s)

	ELLIPTA (N=XXX)	DISKUS + HandiHaler (N=XXX)
At least one Critical Error	XXX (XX%)	XXX (XX%)
Zero Critical Errors	XXX (XX%)	XXX (XX%)
ELLIPTA vs DISKUS + HandiHaler		
Odds Ratio	X.XX	
95% CI	(X.XX, X.XX)	
p-value	X.XXX	

Note: Odds ratio, 95% CI and p-value obtained from a conditional logistic regression model. Subject is included in the model as fixed strata, treatment option, country and period included as fixed effects.

Programming notes: Page by sub-study and assessment

Example : EFF_T05
Protocol : 206215
Population : Intent to Treat

Table X.X
Summary and Analysis of Number of Instructions from the HCP

Sub-study 1: ELLIPTA vs DISKUS + HandiHaler

	ELLIPTA (N=XXX)	DISKUS + HandiHaler (N=XXX)	Difference (ELLIPTA – DISKUS+HandiHaler)
n	X	X	X
Median (95% CI)	XXX (XXX – XXX)	XXX (XXX – XXX)	XXX (XXX – XXX)

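### Censoring three-attempt failures in the T1+T2 Kaplan-Meier analysis makes the plotted curve overstate how many subjects ever reach correct use

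*SAP*

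**What the plan says.** Protocol section 9.1.1 limits teaching: "In total, the HCP can provide instruction in the use of the inhaler up to two times". With the attempt after the leaflet, that makes three attempts per inhaler, and no further assessment follows. Section 9.1.1.3 sets the timing rule: "The clock re-starts when T2 begins and stops once correct use has been demonstrated, or when three failed attempts have been made". Correct use means no critical or non-critical error (note c to the objectives table in Protocol section 4).

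SAP section 8.1.2.4 analyses total time as a Kaplan-Meier outcome. Failures are handled in one line: "T1+T2 is censored for subjects who did not use the inhaler correctly after 3 attempts". The accompanying PROC LIFETEST code treats event code 0 as censored. The survivor functions of the options go on one figure, and "In the above analysis the median time will be taken from the Kaplan Meier model".

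Table shell EFF_T02 in SAP Appendix 12 adds two footnotes. For the two-inhaler options, when one device is used with an error and the other is not, "the time to demonstrate correct use is censored at the total of time taken for both devices". On the median it says: "If more than 50% of the data is censored then the median is not applicable". The shell also counts, for each option, those who did and did not demonstrate correct use. Shell EFF_T05 gives the number and percentage who failed.

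**The concern.** Censoring is meant for subjects whose outcome is unknown because observation stopped for reasons unrelated to it. Here observation stops because the subject failed the last permitted attempt, so the outcome is known. Treating it as unknown removes the subject from the risk set and passes that subject's weight to those who have not yet finished, some of whom succeed later. The survivor curve, read as the proportion not yet using the inhaler correctly, then ends lower than the proportion who really failed.

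The curves are a planned display for a secondary endpoint. A reader will take the end of each curve as the proportion who were ever taught successfully. Failing either device makes the two-inhaler option a failure, so failure rates may well differ between the options drawn together, and so may the amount of failure hidden. No T1+T2 analysis that keeps the failures is planned. The repeat without censoring in SAP section 9.1.1.2 is for T1 only, and it drops those subjects.

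**Working it through.** **Inputs.** The censoring rule, the source of the median and the 50% footnote come from the SAP, and the three-attempt limit from the protocol, as cited above. The sample size of 72 is the planned number completing each sub-study. The documents give no attempt times and no final failure rates, so those below are assumptions.

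**Hand check.** Five subjects: success at 4 minutes, failures at 6, 7 and 8, success at 10.

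- As planned: S(4) = 1 − 1/5 = 0.80. The three failures leave the risk set, one subject remains, and S(10) = 0.80 × (1 − 1/1) = 0. The curve shows everyone succeeding; in fact 2/5 = 40% did. The median is 10 minutes with 3/5 = 60% censored, so the footnote would withhold it.
- Failures placed beyond 10 minutes: S(4) = 0.80 and S(10) = 0.80 × (1 − 1/4) = 0.60. The curve ends at the true failure proportion and has no median, as the footnote says.

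**The 50% footnote in general.** Each success lowers the Kaplan-Meier curve by at least 1/n, so its final value cannot exceed the censored fraction. Below 50% censoring a median therefore always exists (no exception in 20,000 random data sets of 72). Above 50% it may still exist: it did in 7,401 of 9,837 such data sets. For example, 32 successes spread over 3–12 minutes and 40 failures over 4–9 minutes give 40/72 = 55.6% censored and a Kaplan-Meier median of 9.4 minutes. The mismatch runs one way only: the footnote can hide a median but never creates one.

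**Size at n = 72.** Assumed: log-normal times, median 4 minutes for the leaflet attempt and 3 minutes for each instruction cycle, log-SD 0.35, devices independent. Failure on one device is the product of the three per-attempt failure probabilities; on two devices it is 1 − (1 − that)². With success rates 0.4/0.5/0.5: 0.6 × 0.5 × 0.5 = 0.15 for one device and 1 − 0.85² = 0.28 for two. With 0.2/0.35/0.35: 0.8 × 0.65 × 0.65 = 0.34 and 1 − 0.66² = 0.56. Means over 2,000 simulated data sets:

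| Option | Success per attempt | Failing | Kaplan-Meier curve ends at | Overstatement |
|---|---|---|---|---|
| Two inhalers | 0.4/0.5/0.5 | 27.9% | 0.078 | 20.1 points |
| One inhaler | 0.2/0.35/0.35 | 33.9% | 0.091 | 24.8 points |
| Two inhalers | 0.2/0.35/0.35 | 56.2% | 0.279 | 28.3 points |

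The gap does not grow without limit: in an extreme case with 82% failing the curve ended at 0.649, a gap of 17 points.

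**Median, same assumptions, 20,000 subjects per scenario (planned curve against failures kept).**

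- 15% failing, one inhaler: 6.79 v 6.80 minutes.
- 28% failing, two inhalers: 14.66 v 14.90.
- 34% failing, one inhaler: 9.33 v 9.52.
- 57% failing, two inhalers: 21.38 v not reached; the footnote would withhold the 21.38.

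At n = 72 the mean shift was about 0.8 minutes with 38% failing. With true failure near 57% it was about 3 minutes among the minority of data sets in which half or fewer failed.

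**The case against.** The strongest reply is that the plan reports one Kaplan-Meier number, the median, and already guards it. Above 50% failing the footnote withholds it; well below 50% it hardly moves. That stands, and it narrows the point to the plotted curve, and to the median only when close to half fail. The footnote therefore does useful work, since it withholds the medians that lean most on the censoring assumption.

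It is also true that failures are not concealed. EFF_T02 counts them and EFF_T05 gives the percentage, so nothing needs adding there. But a count in a table discloses the failures without correcting the figure.

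Censoring could be defended if the target were the time that would be needed if teaching continued without limit. The documents state no such target, and it would require failures to be no harder to teach than those still in progress, which is implausible.

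A reader might infer that a formal comparison of time is biased, perhaps in favour of ELLIPTA. The documents do not support that. The shell has no p-value, difference or hazard ratio for time, so the comparison is visual. If the two-inhaler option has more failures, the censoring would generally flatter that option and not ELLIPTA. Nor can it be said that the curve must fall to zero or that failures are assumed to succeed soon: they are given the rate of those still at risk, and at n = 72 the simulated curves ended on average at 0.08 to 0.28.

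**Conclusion.** The point holds for the T1+T2 curve. Failure after three attempts is a known end state under the protocol, so censoring it is informative and biases the plotted proportion reaching correct use upwards. The direction follows from the estimator. The size, about 20 to 28 percentage points at 28% to 56% failing, rests on assumed times, success rates and independence between devices. If only a few percent fail, the effect is trivial: with 3.6% failing the curve ends at 0.00 where 0.04 is right, and the median is unchanged at 5.29 minutes.

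The 50% footnote is exact for a curve that keeps failures in the denominator and conservative for the one planned. It should not be counted as a separate error. The primary endpoint and its conclusion are not affected.

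**What to change.** In SAP section 8.1.2.4, keep three-attempt failures as event code 0 but set their time beyond the longest observed T1+T2. This is the same as plotting 1 minus the cumulative proportion correct among all analysed subjects. End the plotted axis at the longest observed time. Take the median from that curve and report it as not reached when fewer than 50% succeed; the EFF_T02 footnote is then correct. Replace the shell note that censors two-inhaler failures at the summed device time, so that one rule covers both options. EFF_T02 is shared with T1 and T2, so say which assessments the new rule covers.

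The cost is one derivation line and small footnote edits. The downside is that curves may plateau and a median may read not reached.

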8.1.2.5. Preference attributes

Secondary Statistical Analyses
Endpoint(s)

 • Treatment preference from questionnaire for number of steps required to take medication • Treatment preference from questionnaire preferred treatment for overall treatment preference.
Model Specification

 • The endpoint of treatment preference will be analysed using the Intent-to-treat population. • This endpoint will be analysed using the Cochran-Mantel-Haenszel test.
Model Checking & Diagnostics

 • Refer to Appendix 9: Model Checking and Diagnostics for Statistical Analyses.
Model Results Presentation

 • The percentage of preference for each specific attribute (i.e., preferring ELLIPTA inhaler, preferring the other inhaler, and no preference) will be summarised by inhaler use sequence. • Subject preference will also be analysed using a Cochran-Mantel-Haenszel test. The Cochran-Mantel-Haenszel test serves as a stratified approximation to Prescott's test, a variation of a one-sample chi-square test that accounts for study inhaler sequence and subjects who indicate no preference. P-values from this analysis will be presented in summary and analysis tables.
SAS Code

 • SAS code for stratified approximation to Prescott's test for each preference question: <pre>ods output CMH = cmhi (where = (upcase(AltHypothesis) = 'ROW MEAN SCORES') keep = AltHypothesis Prob) ; proc freq data = pref_data ; tables seq * pref_ord country / cmh ; run ;</pre> 
Country will be included in the model providing there are sufficient subjects distributed to enable the model to run. If the model will not run with country in the model then country will be removed from the model.
 
pref_ord is derived as shown in Section 11.5.4

9. OTHER STATISTICAL ANALYSES**9.1. Efficacy Analyses****9.1.1. Overview of Planned Other Efficacy Analyses**

The other efficacy analyses will be based on the Intent-to-treat population, unless otherwise specified.

[Table 5](#) provides an overview of the planned other efficacy analyses, with further details of data displays being presented in [Appendix 11: List of Data Displays](#).

Table 5 Overview of Planned Other Efficacy Analyses

	Absolute			
	Stats Analysis	Summary		Individual
	T	T	F	L
Number of critical errors made after Healthcare Professional (HCP) instructions				
The percentage of subjects making at least one critical error after the second instruction from the HCP	Y	Y	Y	
Number of overall errors made				
Percentage of subjects making at least one overall error after the second instruction from the HCP	Y	Y	Y	
Training/Teaching time required				
Time to read PIL(s) (T1)	Y	Y	Y	Y
Instruction time by the HCP (T2)	Y	Y	Y	Y

NOTES :

- T = Table, F = Figure, L = Listing, Y = Yes display generated.
- Stats Analysis = Represents TFL related to any formal statistical analyses (i.e. modelling) conducted.
- Summary = Represents TFL related to any summaries (i.e. descriptive statistics) of the observed raw data.
- Individual = Represents TFL related to any displays of individual subject observed raw data.

Summary statistics will be generated for the amount of time needed to read the PIL(s) (T1) and the total instruction time by the HCP (T2) separately. These will be presented in the same format as the total amount of time taken to demonstrate correct inhaler use.

9.1.1.1. Number of critical errors/overall errors made after 2nd Healthcare Professional (HCP) instructions

Other Statistical Analyses
Endpoint(s)

 • The percentage of subjects making at least one critical error after the second instruction from the HCP • Percentage of subjects making at least one overall error after the second instruction from the HCP
Model Specification, Model Checking & Diagnostics, Model Results Presentation

 • Same method as percentage of subjects making at least one critical error after reading the PIL(s), see Section 7.1.2 • Note this model will only be fitted if there is sufficient data. If there is insufficient data then only summary statistics will be produced.

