7.2. Method of Treatment Assignment

All participants will be centrally randomized using an Interactive Web Response System (IWRS). Before the study is initiated, the log in information & directions for the IWRS will be provided to each site.

Participants will be assigned in equal numbers to one of four sequences for the sub-study they are included on, in accordance with the randomization schedule generated by Clinical Statistics, prior to the start of the study and using validated internal software.

The possible sequences for each sub study are shown in Table 1 and Table 2

Table 1 Sub Study 1 Treatment Sequences

Sequence	Period 1	Period 2	Preference Questionnaire
A	ELLIPTA	DISKUS + HandiHaler	1
B	DISKUS + HandiHaler	ELLIPTA	2
C	ELLIPTA	DISKUS + HandiHaler	2
D	DISKUS + HandiHaler	ELLIPTA	1

Table 2 Sub Study 2 Treatment Sequence

Sequence	Period 1	Period 2	Preference Questionnaire
E	ELLIPTA	Turbuhaler + HandiHaler	3
F	Turbuhaler + HandiHaler	ELLIPTA	4
G	ELLIPTA	Turbuhaler + HandiHaler	4
H	Turbuhaler + HandiHaler	ELLIPTA	3

Study treatments will be dispensed at the study visit summarized in SOA

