7.3. Blinding

This is an open-label study; however, the order of treatment and preference questionnaire answered by a participant will be assigned using an IWRS. The site will contact the IWRS prior to study treatment administration for each participant. The site will record the treatment assignment on the applicable case report form, if required. Potential bias will be reduced by randomising the order of treatment and the preference questionnaire version answered by subjects.

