10.2. Sample Size Determination

The sample size calculation for each sub-study is based on the primary endpoint, the percentage of subjects making at least one critical error in each device combination (Ellipta or DISKUS - HandiHaler or Turbuhaler - HandiHaler) after reading the patient information leaflet(s).

Based on the results from studies 201301 and 201330, a range of critical error rates (at least one critical error using each device after reading the patient information leaflet) for each of the treatment options (ELLIPTA, DISKUS - HandiHaler and Turbuhaler - HandiHaler) were explored.

Using 10000 simulations, a total of 72 subjects in each sub-study will provide at least 90% power to show a statistically significant difference between the critical error rate of each of the paired treatment options (Sub-study 1: Treatment option 1 vs. Treatment Option 2; Sub-study 2: Treatment option 1 vs. Treatment Option 3) assuming the following true critical error rates.

Treatment Option 1:	Treatment Option 2:	Treatment Option 3:
ELLIPTA Critical Error Rate	DISKUS - HandiHaler Critical Error rate	Turbuhaler - HandiHaler Critical Error rate
11%	>=37%	>=37%
10%	>=35%	>=35%
9%	>=34%	>=34%
8%	>=32%	>=32%
7%	>=31%	>=31%
6%	>=29%	>=29%

The error rates for the combined treatment options were based on the studies 201301 and 201330 and a conservative assumption that the critical error rate for the combined treatment was the same as the critical error rate for a single device i.e. subjects who made errors made them on both devices.

Conditional logistic regression and a two-sided 5% significance level were used as the analysis method in the simulations. No withdrawal is expected in this single visit study however up to 80 subjects may be randomised to each sub-study to ensure we have 72 evaluable subjects in each sub-study.

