10.4. Statistical Analyses

10.4.1. Efficacy Analyses

Endpoint	Statistical Analysis Methods
Primary	
The primary endpoint is the percentage of subjects making at least one critical error after reading the PIL(s).
 
This endpoint will be analysed using conditional logistic regression with subject as fixed strata, and treatment option and period as fixed effects. The odds ratio, 95% CI and p-value will be presented for the comparison between treatment options. It will be based on a two-sided hypothesis testing approach of superiority.

Secondary	
The following endpoints will be analysed in the same way as for the primary endpoint if there are sufficient subjects making errors otherwise the data will be summarised only:
 
 The percentage of subjects making at least one critical error after the first instruction from the HCP The percentage of subjects making at least one overall error after reading the PIL(s) The percentage of subjects making at least one overall error after the first instruction from the HCP 
The number of instructions (0, 1 or 2 times) from the HCP which are needed to demonstrate correct inhaler use will be analysed using the Wilcoxon signed rank test.
 
The total amount of time taken to demonstrate correct inhaler use (T1+T2)

Endpoint	Statistical Analysis Methods
	
will be analysed using Kaplan-Meier methods.
 
Treatment preference from questionnaire will be analysed using a Cochran-Mantel-Haenszel test, adjusted for study inhaler use sequence.

Other	
Analysis of the following other endpoints will be defined in the Reporting and Analysis Plan.
 
 • The percentage of subjects making at least one critical error after the second instruction from the HCP • The percentage of subjects making at least one overall error after the second instruction from the HCP • The amount of time taken to read the patient information leaflet and demonstrate correct inhaler device use (T1) • The amount of time taken to be given instruction by the HCP on use of the inhaler and demonstrate correct inhaler use (T2)

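### The preference test omits the randomised questionnaire version; it remains valid, but a list-order stratum would recover a little precision cheaply if list order affects answers

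*SAP*

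**What the plan says.** Protocol 7.2 states: "Participants will be assigned in equal numbers to one of four sequences for the sub-study they are included on". In each sub-study the four sequences cross inhaler order with questionnaire version. In Protocol Appendix 3 the versions are meant to differ only in which treatment option is listed first. Protocol 7.3 presents this as a safeguard for an open-label study: "Potential bias will be reduced by randomising the order of treatment and the preference questionnaire version answered by subjects".

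The analysis uses only half of that randomisation. Protocol 10.4.1 specifies a Cochran-Mantel-Haenszel test "adjusted for study inhaler use sequence". SAP 11.8.1 defines that sequence by inhaler order alone (ELLIPTA first or ELLIPTA second). SAP 8.1.2.5 calls the test an approximation to Prescott's test, "a variation of a one-sample chi-square test that accounts for study inhaler sequence and subjects who indicate no preference", and takes the row-mean-scores p-value from a table of `seq` by `pref_ord`. SAP 11.5.4 codes `pref_ord` as -1 if the first-used option is preferred, +1 if the second-used option is preferred, and 0 for no preference. Country is the only further factor considered. Questionnaire version appears in a listing shell, but in no summary table, stratum or model.

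**The concern.** A factor was randomised to protect the preference answers, and the analysis then ignores it. Because the score is coded by period of use, a pull towards the first-listed option moves `pref_ord` up in half of the sequences and down in the other half. Equal allocation cancels this in the comparison of inhaler orders, but the unstratified variance still counts the spread as noise. At stake is some precision on two secondary endpoints that are reported with p-values. The percentages preferring each option would not change.

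**Working it through.** **The plan's own figure.** The documents give no power or test size for the preference questions. The only power statement, "a total of 72 subjects in each sub-study will provide at least 90% power", concerns the primary endpoint. With errors on the two treatment options taken as independent within subject (an assumption), exact McNemar power is 94-95% across the six rows of the Protocol 10.2 table, which is consistent with it. It says nothing about preference.

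**Inputs.** From the documents: 72 evaluable subjects, so 72/4 = 18 per sequence; the sequence tables in Protocol 7.2; the option order in Appendix 3; the scores in SAP 11.5.4. Assumed: a two-sided 5% level (stated only for the primary simulations), 20% with no preference, and a list effect of *L* = 0 to 20 percentage points moved to the first-listed option.

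**Which way each sequence shifts**

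| Sequence | Used first | Listed first | First-listed option is | Shift in `pref_ord` |
|---|---|---|---|---|
| A, E | ELLIPTA | combination | second-used | up |
| B, F | combination | ELLIPTA | second-used | up |
| C, G | ELLIPTA | ELLIPTA | first-used | down |
| D, H | combination | combination | first-used | down |

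(For F and G, Version 4 is read as intended.)

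**Bias.** With no true preference (40/40/20), the mean score is +2*L* in A and B and -2*L* in C and D. ELLIPTA-first is A + C and ELLIPTA-second is B + D. Each averages (+2*L* - 2*L*)/2 = 0, so the contrast is unbiased.

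**Size.** The planned test uses the total variance, 0.8. The contrast actually varies with the within-group variance, 0.8 - 4*L*². Hence

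size = 2{1 - Φ(1.96 × √[0.8/(0.8 - 4*L*²)])}.

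Among subjects with a preference, the share choosing the first-listed option is (0.4 + *L*)/0.8.

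| *L* (points) | Share choosing first-listed | 0.8 - 4*L*² | Size by formula | Size simulated, planned |
|---|---|---|---|---|
| 5 | 56.25% | 0.79 | 4.86% | 4.9% |
| 10 | 62.5% | 0.76 | 4.43% | 4.4% |
| 15 | 68.75% | 0.71 | 3.75% | 3.7% |
| 20 | 75% | 0.64 | 2.84% | 2.7% |

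Stratified into A/B v C/D, simulated size is about 5% throughout.

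**Power (simulated, planned to stratified)**

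| *L* (points) | 50% v 30% | 55% v 25% |
|---|---|---|
| 0 | 47.9 to 48.0% | 82.7 to 82.7% |
| 5 | 47.5 to 48.0% | 83.0 to 83.6% |
| 10 | 47.7 to 49.9% | 83.5 to 85.1% |
| 15 | 47.3 to 52.5% | 84.3 to 87.8% |
| 20 | 47.3 to 57.5% | 85.8 to 92.0% |

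At 65% v 15% both tests exceed 99% at every list effect tried (0-15 points).

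**Choice of stratum.** Stratifying by version number (A/D v B/C) leaves size and power within 0.2 points of the planned test, because each such stratum mixes upward and downward shifts. Only A/B v C/D takes the shift out of the variance.

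**Sensitivity.**
- Reversing the sign of the effect (favouring the last option) gives the same result: at 15 points, size 3.7 to 5.0%.
- With 10% no preference, and 60% or 70% of those with a preference choosing the first-listed option, planned size is 4.5% or 3.4%, against 5.0% stratified.
- With evaluable counts of 16/20/20/16 in A-D and the same two list effects, planned size is 5.0% and 4.7%, so imbalance of that degree does not inflate it.

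**Country.** With country kept as a stratum and no list effect, adding the list-order stratum changes power from 47.8 to 47.1% and from 82.2 to 81.6%. At 5 points the two are about level (47.0 to 47.1%; 82.5 to 82.4%).

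**The case against.** The strongest reply is that nothing is broken. The randomisation does what Protocol 7.3 says it is for, the SAP follows the protocol and a named method, no power is claimed for preference, and any error is on the conservative side. All of that stands.

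The larger gains also need a large list effect. Twenty points means that 75% of subjects with a preference choose whatever is listed first, on a two-question form about inhalers they have just used. At 5 points the gain is about half a point, and under strong preference there is none. That stands too, and it sets the severity.

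Four stronger readings are tempting, and the documents do not support them:

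- *The preference p-values are biased or anti-conservative.* Under the two-level sequence of SAP 11.8.1 they are not. The risk would arise only if `seq` were coded as the four randomised sequences. The row-mean-scores test would then have 3 degrees of freedom and, with no device preference and 10% no preference, would reject 23% or 79% of the time when 60% or 70% of those with a preference choose the first-listed option.
- *The planned test loses power as list order matters more.* When a fixed number of points moves, its own power is flat or rises (see the table). If the effect acts on the logit scale, planned power does fall, but so does stratified power, because average preference is diluted. At an average 65% before the effect, the two are 65.4 v 66.8% and 54.5 v 60.4% for the same two list effects. The shortfall is always relative to the stratified test.
- *The sponsor expects a list-order effect.* Protocol 7.3 refers only to potential bias and names no mechanism.
- *The change is free.* That holds without country strata. With them it can cost a fraction of a point.

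**Conclusion.** The point holds as a cheap improvement of low severity. The planned preference test is valid. If list order influences answers, it is conservative and gives up some power relative to a test that uses the factor already randomised. On the assumptions above, size is about 4.9%, 4.4%, 3.7% and 2.7% at 5, 10, 15 and 20 points. The power forgone is about 0.5-0.7, 2, 5 and 10 points at 50% v 30%, and about 0.5, 1.6, 3.6 and 6 points at 55% v 25%. Both the list effect and the no-preference rate are assumptions.

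For sub-study 2 the gain also assumes that Version 4 is corrected. As printed in Protocol Appendix 3 it offers the DISKUS and HandiHaler pair to Turbuhaler subjects (sequences F and G). If that moved answers, so that 60% of Version 4 respondents with a preference chose ELLIPTA under no true preference, both the planned and the stratified test would reject about 12-13% of the time. Stratification does not repair that.

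**What to change.** In SAP 8.1.2.5 and 11.5.4:

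1. Derive `listord` = 1 for sequences A, B, E, F (second-used option listed first) and 2 for C, D, G, H (first-used option listed first). Do not use the version number as the stratum.
2. Run the row-mean-scores test as `listord * seq * pref_ord`.
3. If country is retained, use `country * listord * seq * pref_ord`. The printed `seq * pref_ord country` does not make country a stratum, whereas the SAP Appendix 9 code does.
4. State that `seq` has two levels, inhaler order only.
5. Correct or reconcile Version 4 in Protocol Appendix 3 with the sub-study 2 treatments, and confirm which wording was given to subjects.

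The cost is one derived variable and one extra term. There is no power loss without country strata, and about 0.5-0.7 points if country is also a stratum and list order has no effect. The change should be made before database freeze, the SAP's own deadline for analysis decisions.
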